### **6.3 Control of Bias and Confounding (if applicable, typically observational study or if randomization is not taking place)**

All statistical models by the Pennsylvania study team will be adjusted for age and sex. We will consider other relevant confounders depending on the investigated outcome variable. Genetics analyses by FAA CAMI may employ a variety of exploratory models.

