### 3.2 Allocation to Interventional Group

We will investigate participants in 6 groups of 4 subjects each. Each subject of a group will be exposed to the same condition in each study night, and each subject will receive each exposure— in a randomized and balanced fashion – according to the randomization table below.

Group	Night 1	Night 2	Night 3	Night 4	Night 5	Night 6	Night 7
1	Adaptation	A	B	C	D	E	F
2	Adaptation	B	D	A	F	C	E
3	Adaptation	C	A	E	B	F	D
4	Adaptation	D	F	B	E	A	C
5	Adaptation	E	C	F	A	D	B
6	Adaptation	F	E	D	C	B	A

Please note that in this randomization paradigm, each exposure appears in each position exactly once, and is preceded by each other exposure exactly once. The letters A-F will be randomly assigned to the exposure conditions 1-6 listed in 3.1 above by the principal investigator using a random number generator. Study participants and staff will be blinded to the condition of each night. Staff will only be unblinded after the start of the measurements each night (i.e., after subjects went to bed) so that the correct playback of the conditions can be monitored.

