### 4.2 Total Number of Subjects and Sites

The enrollment goal of the study is N=24 subjects with completed evaluable data. However, if a subject withdraws or is withdrawn from an in-laboratory study run, we will need an additional back-up run(s), each of up to n=4 individuals to account for the loss of data. Therefore, it is expected a total of N=28 subjects may begin the in-lab phase, thus allowing for completed evaluable data on up to ~n=27 subjects. Recruitment is expected to end when approximately 84 subjects have been screened. It is expected that approximately 84 subjects will need to be screened in order to enroll 24 evaluable subjects. The University of Pennsylvania is the only site enrolling participants for this research protocol.

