- f. Subjects will complete a test drive on the driving simulator to check for signs of motion sickness, as those who are unable to complete the task for physical reasons will not be eligible for the in-lab study.
- g. Subjects will receive a REDCap link to the daily morning questionnaire (and physical copies of the survey to use as a backup if unable to connect to the internet) to complete at home, which take about 5 minutes each morning, and their activity will be monitored by a small device worn on the wrist called an actiwatch (which is about the size of a wrist watch) during the subsequent 7-14 days, until the second laboratory appointment. In addition, a Pulse Oximeter (a small device that is worn on the fingertip to measure pulse and oxygen levels) will be distributed for use on one night at home.

Subjects meeting all screening eligibility criteria for the study will be scheduled for a second 4-hour screening approximately 7-14 days after screening session #1.

**Screening session #2** includes the following:

- a. An additional blood and/or urine sample collection if necessary.
- b. The History & Physical (H&P) with EKG at CHPS, if unable to schedule for screen #1.
- c. Review of actiwatch, Pulse Oximeter, and sleep log.
- d. Initial training related to the Cognition test battery.
- e. Scheduling of the 7-night in-laboratory phase of the study.
- f. Subjects will continue to wear the wrist activity monitor and complete the morning survey on REDCap.

Participants meeting all inclusion/exclusion criteria will be enrolled in the 7-night in-laboratory phase of the study. Subjects will be scheduled for the 7-night in-laboratory phase of the study in groups of up to 4 until total study enrollment (N=24) is achieved.

In the event that we have five fully qualified participants for one study run, we may see if one of the subjects is willing to serve as a backup subject. The subject would still arrive to the lab on Night 1 and be available to participate for the full 7-night study if any of the four primary subjects is unable to participate.

If the backup subject **IS** needed, they will continue the study as a primary subject.

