### **6.2 Statistical Methods**

The primary outcome of the study is: time spent in slow wave sleep (SWS) plus rapid eye movement (REM) sleep during an 8-hour sleep opportunity (11 pm – 7 am). We will use linear mixed effect regression models with random subject intercept to investigate whether SWS+REM duration differs significantly between the 6 study conditions (we will use non-linear mixed effect models for binary secondary outcomes). If  $p < 0.05$  of the omnibus test, we will perform post-hoc tests contrasting all conditions with each other. Our primary contrast of interest for which the study was powered is the difference in SWS+REM duration in aviation noise nights with and without broadband noise of 50 dB.

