#### **6.3.2 Analysis of Primary Outcome of Interest**

Our primary contrast of interest is the difference in SWS+REM duration in aviation noise nights with and without broadband noise of 50 dB. In the mixed model framework, this is equivalent to a paired t-test.

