### **10.4 Informed Consent Process / HIPAA Authorization**

Informed consent will be obtained from adult subjects who are competent to give it. All verbal and written communication will be in the English language. Informed consent forms will be given and signatures will be obtained before the start of the study. After consent is given, it can be withdrawn at any time and the subject can be removed if they choose. In the event that a subject withdraws their consent, data collected up to the point of withdrawal may be retained as it would not be possible to completely eliminate all data collection. In order to avoid potential coercion, Penn employees, Penn students, educationally or economically disadvantaged persons will not be specifically targeted or unjustly excluded. Subjects will be able to sign their consent form after an individual meeting where they will be able to ask any questions they may have to a member of the research team. There is no time limit to this session which will be held in a private room.

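### Study night is balanced by the Williams square in 3.2 but is not a pre-specified model term, so any night drift costs power and, if rows become unequal, can shift contrasts

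*Combined protocol and SAP*

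**What the plan says.** **Design.** Section 3.2 uses a six-row square, one row per group of four, in which "each exposure appears in each position exactly once, and is preceded by each other exposure exactly once". Letters are assigned to conditions at random.

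**Analysis.** Section 6.2 specifies "linear mixed effect regression models with random subject intercept" to compare the six conditions, with post-hoc contrasts only if the omnibus test gives p < 0.05. Section 6.3 states that "All statistical models by the Pennsylvania study team will be adjusted for age and sex", and then: "We will consider other relevant confounders depending on the investigated outcome variable". Section 6.3.2 says of the primary contrast (AN+BN50 against AN): "In the mixed model framework, this is equivalent to a paired t-test". Night, period or order is not named as a model term anywhere.

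**Drop-outs.** Section 4.2 says that if a subject leaves a run, "we will need an additional back-up run(s), each of up to n=4 individuals to account for the loss of data". It expects up to 28 starters and about 27 evaluable subjects. The table in 3.2 has six rows and assigns none to a seventh run. Section 5.1 provides for a fifth person to attend on night 1 and "be available to participate for the full 7-night study if any of the four primary subjects is unable to participate". Under 10.4, "data collected up to the point of withdrawal may be retained".

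**The concern.** The square protects the condition contrasts from a trend over nights only through balance. Age and sex are constant within a subject, so they cannot absorb such a trend, and neither can a random intercept. An analyst who follows 6.2, 6.3 and 6.3.2 as written leaves night variation in the residual.

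Two things are at stake. With complete data, a night trend inflates the standard error of the primary contrast, and the omnibus test that must be passed first uses the same residual. With unequal rows, part of the trend enters the contrast itself. The clause on other confounders permits a night term but leaves the choice open, outcome by outcome.

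**Working it through.** **Inputs from the documents:** N = 24, effect size 0.60, two-sided 5%, at least 80% power (6.1); the square (3.2); about 27 evaluable subjects (4.2). **Assumptions, because the documents give no figure:** linear drift b = 0.1, 0.2 or 0.3 residual SD per night; additive night effects; independent residuals; 0.60 measured in SDs of the paired difference (6.1 does not say which SD), which is 0.60 × √2 = 0.85 residual SD.

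**1. The plan's own figure.** Noncentrality is 0.60 × √24 = 2.94. A paired t-test on 23 df gives 80.4%, and 24 is the smallest N that reaches 80%. The mixed model has 144 − 24 − 5 = 115 error df and gives 83.0%. Adding night leaves 110 df and 83.0%. The stated power reproduces.

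**2. The square.** Each letter occurs once per night, all 30 ordered neighbour pairs occur once, and the night lags sum to 0 over the six rows for all 15 condition pairs. With complete data the bias is therefore exactly 0.

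**3. Complete data, mixed model without night.** The between-night variance is V = b² × 35/12. It is left in the residual, so the reported SE is multiplied by √(1 + (144/115)V). The true SD of the estimate stays at √(2/24) = 0.289 residual SD.

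| Drift per night | SE factor | Type I error | Power, no night term | Power, with night |
|---|---|---|---|---|
| 0.1 | 1.018 | 4.6% | 82% | 83% |
| 0.2 | 1.071 | 3.6% | 79% | 83% |
| 0.3 | 1.153 | 2.4% | 74% | 83% |

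**4. Complete data, paired t-test of 6.3.2.** Only the two nights being compared matter, so the SE factor is √(1 + (24/23) × b² × Q/2), where Q is the mean squared lag of the pair. From the table in 3.2, Q is 3 for six pairs, 8.67 for six and 11.67 for three. From the 80.4% baseline, noncentral-t power with the critical value multiplied by this factor is:

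| Drift per night | Q = 3 | Q = 8.67 | Q = 11.67 | Mean of 15 pairs |
|---|---|---|---|---|
| 0.1 | 80% | 79% | 79% | 79% |
| 0.2 | 79% | 75% | 73% | 76% |
| 0.3 | 76% | 69% | 64% | 71% |

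Which column applies to AN+BN50 against AN depends on the letters drawn.

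**5. Unequal rows, no night term.** The imbalance of a contrast in nights is Σ(n_g × lag_g)/N, and the bias is b times that. The largest lag in a row is 5.

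| Case | Median | Maximum | Maximum bias at b = 0.2 |
|---|---|---|---|
| One-for-one replacement, same row | 0 | 0 (0.16 if the leaver's partial nights are used) | 0 (0.03 SD) |
| One lost, N = 23 | 0.09 | 5/23 = 0.22 | 0.04 SD |
| N = 27, depleted row repeated | 0.22 | 3 × 5/27 = 0.56 | 0.11 SD |
| N = 27, another row repeated | 0.33 | (4 × 5 + 5)/27 = 0.93 | 0.19 SD |

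The 0.93 occurs in 6 of 450 row-and-pair combinations. There, at b = 0.2, type I error is about 8%. In the median case for another row, bias is 0.07 SD and type I error 4.1%. With night in the model, the bias from additive night effects is 0 in every case.

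**The case against.** The best case against the point is that nothing in the stated plan is wrong. Balancing position by design is an accepted way to handle order, 6.3 leaves room for night, and with complete data the test does not exceed its nominal size under the assumptions used here. An adaptation night comes first, and the documents report no night trend. The two larger drifts total 1.0 and 1.5 residual SD over nights 2 to 7, which exceeds the whole powered effect of 0.85; at the smallest drift the loss is about one percentage point. The bias needs real drift, unequal rows and an unfavourable letter draw together. The night-1 stand-in and same-row replacement would avoid much of it.

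All of this stands, and it limits the weight of the point. It does not remove it. The paired t-test starts at 80.4%, so even a small drift takes it to about the stated 80% or just below, and unequal rows are foreseen in 4.2. Permission to consider night is not pre-specification.

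A reader might infer that the primary analysis is biased or the power claim wrong. The documents support neither: the square gives zero bias with complete data, and the 80% reproduces. A reader might also take 0.19 SD and 8% as the expected harm. They are a rare worst case that needs a back-up run in a different row, which no section states.

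**Conclusion.** The point holds as a low-cost improvement to a sound design. With 24 complete subjects the contrasts are unbiased, and the cost of omitting night is power: about 1, 4 or 9 percentage points in the mixed model (83% to 82%, 79% or 74%) at the assumed drifts. For the paired t-test the average loss is similar. With unequal rows the primary estimate also shifts for the one letter assignment drawn, by at most 0.04 SD with one subject lost and 0.2 SD drift per night. Over random letter assignments the shift averages zero.

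These results rest on assumed drift sizes and on night effects that are additive with independent residuals. The four subjects of a group share each night. If a group-night carries its own effect, with an assumed shared SD of 0.3 residual SD, type I error is about 8% with or without a night term. That is a separate issue, and the 5% figures given for the model with night should not be read as covering it.

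**What to change.** In 6.2/6.3, state that all within-subject models run by the Pennsylvania team include condition and study night (2 to 7, categorical) as fixed effects, with age, sex and a random subject intercept, and that all contrasts are taken from this model. Reword the paired t-test sentence in 6.3.2 to match.

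Stating in 3.2 which row a back-up run follows is optional. It makes the allocation explicit, but once night is in the model, additive night bias is removed whichever row is repeated.

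The cost is one sentence and one rewording. Night is already recorded. The term uses 5 of 115 error df, and with no drift power is 83.0% with or without it.

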### Evening and Morning Procedures

Subjects will arrive in the lab around 8 pm in the evening and they will be able to leave the lab around 9 am in the morning (by 10 am at the latest). As our noise exposures can affect sleep and impair recuperation to some degree, participants will be informed in the consent form that they should not operate heavy machinery during the study. We will also offer a cab for those who would otherwise use a car to come to the lab. We will provide snacks in the evening and a light breakfast in the morning. Subjects can shower in the morning (after all tests) if they wish.

In the evening (before bed) and in the morning (after waking up), subjects will do the following:

- (1) Blood draw (for gene expression analyses to be performed by the FAA Civil Aerospace Medical Institute (CAMI); morning only).
- (2) Fill out surveys that ask about sleepiness, mood states, the previous day or the previous night;
- (3) Cognition test battery (10 cognitive tests);
- (4) Driving simulator task;
- (5) Hearing test;
- (6) Blood pressure measurement; and
- (7) Resting ECG measurement.

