### **3.4.2 Secondary Study Endpoints**

We plan to investigate the following secondary endpoints in relation to the different noise exposure conditions.

Sleep-related secondary endpoints:

1. Time spent awake and in different sleep stages (N1, N2, N3, REM)
2. Sleep fragmentation, i.e. number of awakenings and EEG arousals per hour sleep
3. Latency to sleep stages N2, N3 and REM
4. Frequency, density and amplitude of sleep spindles, K-complexes and vertex sharp waves
5. Power-spectral density in alpha, beta, theta and delta frequency bands
6. Event-related analysis with the following endpoints
  - a. Awakening
  - b. EEG arousal
  - c. Odds Ratio Product (ORP)

Non-sleep-related secondary endpoints:

1. Cognition test battery performance
  - a. One standard speed and one standard accuracy outcome for each of the 10 tests
  - b. Accuracy, speed and efficiency across cognitive domains
2. Driving simulator performance
  - a. Standard deviation of lateral position (i.e., continuous location of a vehicle with respect to a lane reference)
  - b. Standard deviation of speed
3. Hearing test
  - a. Threshold shift in dB at the following frequencies: 500 Hz, 1,000 Hz, 2,000 Hz, 4,000 Hz, 6,000 Hz, and 8,000 Hz
4. Blood test
  - a. Change in RNA expression levels

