## 4 Study Population and Duration of Participation

### 4.1 Duration of Study Participation

The study will last approximately four weeks, including 2 days of screening ~1-3 weeks prior to the in-lab phase (each session lasting approximately 4 hours), up to a 21-day at-home phase, and a 7-night period of staying in the laboratory overnight (during which time the participants will be able to leave during the day to resume normal activities).

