### **6.1 Sample Size and Power Determination**

Power calculations were conducted using PASS (Version 21 NCSS), assuming a 5% type I error rate and using two-sided hypothesis tests. We used data collected in the AIRORA study performed at DLR to inform power calculations. With a proposed sample size of 24 subjects, we expect to have at least 80% power to detect a medium effect size of 0.60 for the mitigation effect of BN on our primary outcome due to aviation noise.

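### Secondary outcomes: the models for morning cognition, driving and hearing should use the pre-exposure evening value, centred within subject; age and sex cannot reduce within-subject error

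*Combined protocol and SAP*

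**What the plan says.** **Model.** Section 6.2 specifies a linear mixed model with a random subject intercept for the six conditions. The opening of Section 6 says that the secondary outcomes are analysed along the same lines, with a multiplicity adjustment. Section 6.3 adds: "All statistical models by the Pennsylvania study team will be adjusted for age and sex". Its next sentence allows other confounders, depending on the outcome, without naming any.

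**Data.** Section 3.1 (Evening and Morning Procedures) says: "In the evening (before bed) and in the morning (after waking up), subjects will do the following". The list includes surveys, the cognitive battery, the driving task, the hearing test and blood pressure. Section 3.3 confirms evening and morning administration for each of these. Noise starts only after lights out (3.1, Noise Exposure), so the evening value precedes that night's exposure. By day, "participants will be able to leave during the day to resume normal activities" (4.1), and the surveys ask about naps, exercise and caffeine (3.3).

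**Endpoints.** The non-sleep secondary endpoints in 3.4.2 are "Cognition test battery performance", driving simulator performance, a hearing threshold shift and RNA expression. The mood and sleepiness scales are not listed there; they serve the subjective well-being objective in 2.2. Blood pressure appears in neither place.

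**The concern.** In a crossover, the precision of a condition contrast depends on the variation between one subject's nights. The random intercept already removes stable differences between subjects. Age and sex are also stable, so the two named covariates leave the relevant error term untouched.

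The evening value is different because it varies from night to night. It can reflect what the subject did that day, and it is fixed before the night's condition begins. Adjusting for it therefore cannot remove the effect of that condition. The plan spends a 20-minute battery with its survey, a 15-minute drive, audiometry and questionnaires on each evening, but assigns the results no role in the analysis. At stake is precision on next-day outcomes that share 24 subjects and a multiplicity correction.

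**Working it through.** **1. The plan's own power figure.** Section 6.1 gives the inputs: "assuming a 5% type I error rate and using two-sided hypothesis tests", "With a proposed sample size of 24 subjects" and "at least 80% power to detect a medium effect size of 0.60". Section 6.3.2 equates the primary contrast with a paired t-test. Taking 0.60 as a multiple of the SD of the paired difference (the standardiser is not stated):

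- noncentrality = 0.60 × √24 = 2.94
- power on 23 df, two-sided 5% = 80.4%

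The stated figure reproduces. In the full mixed model, residual df are 144 observations − 24 subjects − 5 condition terms = 115, and the same effect has 83.0% power. I use 83.0% as the reference for a hypothetical secondary contrast of 0.60, before any multiplicity adjustment.

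**2. Effect of an evening covariate.** Let r be the correlation between evening and next-morning values after removing each subject's mean. The documents do not give r, so it is an assumption shown over a range.

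- Centred covariate: residual variance is multiplied by 1 − r², the standardised effect becomes 0.60/√(1 − r²), and the equivalent sample is 24/(1 − r²). Residual df fall to 114.
- Raw morning-minus-evening difference (equal variances assumed): residual variance is multiplied by 2(1 − r).

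| Assumed r | Covariate: variance | Power | Equivalent n | Raw difference: variance | Power |
|---|---|---|---|---|---|
| 0.1 | ×0.99 | 83.4% | 24.2 | ×1.80 | 58.4% |
| 0.3 | ×0.91 | 86.3% | 26.4 | ×1.40 | 69.3% |
| 0.5 | ×0.75 | 92.0% | 32.0 | ×1.00 | 83.0% |
| 0.7 | ×0.51 | 98.3% | 47.1 | ×0.60 | 96.4% |

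**3. Cost if the covariate is useless.** Estimating one more coefficient inflates the variance by about 115/114 = 1.009. The table's powers count the lost df but not this inflation, so they are slightly favourable. Setting (1 − r²) × 115/114 = 1 gives r² = 1/115, so break-even is at r of about 0.09. At r = 0.1 the covariate is roughly neutral.

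**4. The form of the covariate.** The 24 × 6 design was simulated with 400 runs per setting, equal evening and morning variances, and a share of 0.7 of total variance lying between subjects. Squared standard errors relative to the model without the evening value were:

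| r | Uncentred | Centred | Raw difference |
|---|---|---|---|
| 0 | 1.08 | 1.01 | 1.94 |
| 0.3 | 1.02 | 0.92 | 1.37 |
| 0.5 | 0.83 | 0.75 | 0.97 |
| 0.7 | 0.54 | 0.51 | 0.59 |

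An uncentred value forces one slope on both the between-subject and the within-subject relation, and at low r it loses precision. The centred form is close to neutral at worst.

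**5. Order balance.** In the table in 3.2, each letter occurs once in each position and all 6 × 5 = 30 ordered pairs occur once, as the plan claims.

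**The case against.** The strongest reply is that 6.3 leaves the covariate list open, that the balanced design needs no adjustment for validity, and that the gain rests on a correlation nobody has supplied. Much of that stands, and it rules out several stronger readings.

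- **A reader might infer that only age and sex will be used.** The text does not say so, because further confounders may be added. But in a balanced crossover the evening value is a precision covariate rather than a confounder, so that sentence does not clearly cover it. Nor does it settle the form, on which gain or loss depends.
- **A reader might infer that mood and blood pressure are secondary endpoints being analysed inefficiently.** Section 3.4.2 lists neither. Mood comes in through an objective. Blood pressure has no stated analysis.
- **A reader might infer that hearing has no baseline.** The endpoint is a shift, so a reference is implied. What is missing is which one: 3.3 provides both a screening test and a same-evening test.
- **A reader might infer bias from practice or carryover.** The order table largely balances position and preceding condition. A practice trend is more directly handled by a night term, and 3.4.2 ties the cognition outcomes to a cited paper on practice and stimulus-set adjustment. An evening value may carry some effect of the previous night, which should be acknowledged, but the case here rests on precision.
- **A reader might infer a guaranteed gain.** At r near 0.1 there is essentially none.

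**Conclusion.** The point holds as a low-cost improvement to the secondary outcomes; it does not identify an error. The plan collects a pre-exposure measurement before each condition night for cognition, driving, hearing and mood and gives it no place in the stated model, while the covariates it does name cannot reduce within-subject error.

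The saving in residual variance is about 1% to 49% for assumed r between 0.1 and 0.7, against a cost of about 1% in squared standard error if r is zero. These figures assume a linear relation and a covariate centred within subject; the comparison with a raw difference also assumes equal evening and morning variances. Sleep and RNA outcomes have no evening value, so the primary endpoint and its power do not change. The tests as planned remain valid without the change.

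**What to change.** Add to 6.3, before any outcome data are examined, wording such as:

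> Models for morning cognition and driving outcomes, and for KSS, POMS and PANAS if analysed, will include the evening value of the same measure taken before that night's exposure. It will be entered as two terms: the subject's mean over the six condition nights and the nightly deviation from that mean. The reference for the hearing threshold shift is the same evening's test; the morning threshold will be modelled with the evening threshold entered in the same two terms, not as a raw difference.

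State also that the evening value may reflect the preceding night's condition. Blood pressure needs the same treatment only if it is to be analysed.

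The cost is a few sentences and one within-subject degree of freedom per model (115 to 114). No new data are needed. Fixing the covariate in advance also avoids choosing it outcome by outcome once results are known.
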